5.5 Measurement

Outcomes and covariates collected during study visits are described below:

Patient Characteristics. During interviews, RCs will collect patient socio-demographic and health characteristics (including comorbidity and health status) and will administer brief measures of social support, anxiety and depression (PROMIS), and health literacy (3-item screener). These measures have been used in prior studies by our team, are validated, and have been shown in the scientific literature to influence medication use.

Regimen Characteristics. At each interview, RCs will review the medication list in the patients' EHR and those reported by patients. We will use a structured protocol from prior studies to identify medications no longer taken and as well as those prescribed but not on the list. Final medications will be grouped by drug class. Regimen complexity will be calculated using the validated Medication Regimen Complexity Index.

Intermediary Outcomes. We will assess a series of intermediary outcomes designed to determine if the TEAM strategy can reduce patient burden and challenges associated with medication self-management and increase patient engagement in care. Specifically, the Healthcare Task Difficulty (HCTD) scale, an 8-item measure in which patients rate difficulty of particular healthcare tasks (e.g. administering medications) will be administered, along with the Treatment Burden Questionnaire (TBQ). The TBQ assesses the workload of being a patient and its effect on quality of life, and is composed of 15 items measuring burden associated with treatment self-management (e.g. taking medicine and following doctors' advice), issues related to healthcare visits including laboratory tests, arranging appointments, and costs. We will also assess health management related to financial barriers and different tools that may help a patient take their medication. Finally, we will measure self-efficacy using the Self-Efficacy for Managing Chronic Disease tool, a widely-used 6-item scale and patient engagement via our team's validated tool, the Consumer Health Activation Index (CHAI). We will assess patient experience by asking questions on interactions with their provider, pharmacist, and specifically about the TEAM intervention.

Effectiveness Outcomes.

STU#: STU00209066

Healthcare provider counseling

We will ask patients (yes/no) whether their prescriber/nurse/pharmacist counseled them about their medications. We will also ask the Health Literacy supplemental items of the Consumer Assessment of Health Providers Survey (CAHPS) to evaluate the extent and quality of provider verbal counseling on Rx medications.

For the outcomes described below, we only include chronic Rx medications. Though we document them, we exclude PRN or limited duration drugs, as adherence concerns are different. All of these measures have been used in multiple studies by our team; results have been published extensively.

Medication Reconciliation

At each interview, commissions (medications listed in the EHR and the patient reported not taking) and omissions (patient reported medications not in the EHR) will be calculated based on medication lists and patient self-report.

Medication knowledge. Medication-specific knowledge will be measured through a series of open-ended questions, capturing patients' knowledge of each of their medication's: 1) indication for use and 2) risks, warnings or potential side effects. Answers will be qualitatively reviewed and independently scored as correct/incorrect by two RCs according to medication information provided from ACCESS and Walgreens. For any that the RCs do not have information on or any with discordance between RCs, a pharmacist will qualitatively review and independently score as correct/incorrect.

Medication dosing errors. We will use a 24-hour recall procedure utilized extensively by this team in prior and current studies to assess Rx dosing errors. At each interview, RCs will review medications reported as taken by the patient and those listed in the EHR to create a final list of medications prescribed to the patient. RCs will then ask patients to report, one by one, how they took each medication over the past 24 hours. Patients will be asked to specify the amount taken (i.e. dose) and when taken (to determine frequency and interval between doses). Patients will be asked to report whether this was how the medication was prescribed, and if not, will be queried: 1) to determine the reason for not taking the medication as prescribed (i.e. forgetfulness, ran out of medication) and 2) to describe how the medication *should* be taken. Data from this exercise will be used to assess correct dosing (yes/no) based upon the instructions for each medication. It will also be used to calculate regimen consolidation, or the total number of time points throughout the 24-hour period that a patient reported taking one or more medicines (count variable, range: 1-24).

Medication adherence. Adherence will be measured using: 1) the Ask-12 survey and 2) the proportion of days covered (PDC) according to pharmacy records. The Ask-12 is a brief measure of adherence that covers three domains: inconvenience/forgetfulness, treatment beliefs and behavior. In prior studies, the tool demonstrated good internal consistency reliability (Cronbach's α 0.75) and test-retest reliability (intraclass correlation 0.79); convergent validity was also

STU#: STU00209066

demonstrated through correlations with multiple other measures (Morisky, SF-12) and pharmacy claims data. Ask-12 scores range from 12-60, with higher scores indicating poorer adherence. PDC will be calculated by summing the number of days' supply obtained by a patient during a given time period and dividing by the number of days for which the medication was prescribed. For each patient, we will assess adherence within drug class. If a patient fills a prescription for a drug and switches to another drug within the same class, all prescriptions will be summed in the numerator. Adherence will be treated continuously and dichotomously (yes/no; PDC at disease-specific threshold based on Pharmacy Quality Alliance (PQA) standards). PDC data will be automatically obtained from Walgreens as part of the TEAM study.

Clinical Markers. We will abstract relevant clinical markers (e.g. HBA1c for patients with diabetes, LDL cholesterol for patients with hypercholesterolemia, blood pressure for patients with hypertension). Multiple blood pressure measures will be averaged for analyses in accordance with current protocols.

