4.0 Study Intervention

4.1 TEAM Intervention Arm

Read/write EHR access with established Epic security points will be granted by ACCESS to Walgreens, with permission to more fully access the EHR only for those patients who have consented to the study and are specifically randomized to the TEAM study arm. These individuals will be referred to a designated Walgreens pharmacist using a report issued by the Walgreens Research Analytics Team, which will include Proportion of Days Covered (PDCs) for prescribed medications in the following therapeutic medication classes: hyperlipidemia, hypertension, diabetes, multiple sclerosis, hepatitis C, and HIV. Pharmacists will also be able to view a patient's record (e.g. problem list, medication list, visit diagnoses, clinic notes, orders, etc.) and, with write access, Walgreens pharmacists will be able to initiate medication

STU#: STU00209066

reconciliation activities, including adding notes in their medication list for the prescriber, requesting the removal or discontinuation of prescribed drugs that patients report they are no longer taking and adding medications omitted from the ACCESS primary care provider's list. Any medications added by the pharmacist will appear in the chart as "Patient-reported". Any addition of medications or notes to the medication list, will require the acknowledgment of the prescribing physician (Epic security point #282). The pharmacist will also be granted the capability of adding clinic notes and secured messaging to prescribers (Epic security point #77). For direct communications, as with notifying a prescriber of an unfilled order, a secured EHR inbox message will be sent by the pharmacist. This was viewed by ACCESS and Walgreens as the best means for getting the immediate attention of a prescriber. Figure 6 depicts the TEAM Intervention work flow. Specific TEAM activities and their timing are described below:

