Pharmacists will document the CMR in real-time based on current practices and chart in the EHR afterwards (add any new medications to the medication lists, send secure messages to providers, create clinic notes). Any medications proposed to be added or discontinued from the medication list will be flagged and accompanied by a clinic note, requiring the prescriber to acknowledge the note and update the list. The pharmacist also will have the option in Epic to mark in the medication list if the patient reports not taking it at this time even though it is prescribed (e.g. intentional non-adherence). Any proposed reconciliation of the medication list will be accompanied by a highlighted note/justification in the EHR. In a similar manner, secured Epic EHR in-basket messages will be sent to prescribers if an ADE or serious side effect is detected, or premature discontinuation of a medication is reported. The pharmacist will generate an overall summary of the CMR, including any clinical recommendations or commentary on patient adherence, in a clinic note, which will populate as a patient encounter in the chart. Ideally, the

STU#: STU00209066

CMR will be completed one month post baseline interview and will take place before the follow-up interview conducted at two months.

Additional contact may be made if the Walgreens pharmacist were to discover a patient was recently hospitalized or if serious adherence concerns were detected from pharmacy fill data (see below).

At 6 months, the Walgreens Research Analytics Team will send an additional Adherence Report for patients in the TEAM intervention to the community pharmacist. The pharmacist will review the report and if a patient has poor adherence for at least one medication, they will initiate Therapy Management Review (TMR). This is a call from the pharmacist to the patient checking in specifically about the medication(s) for which they have poor adherence. After the TMR call, the pharmacist will create notes and send an in-basket message to the prescriber as necessary.

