17.0 Data Management and Confidentiality

17.1 Analysis Plan

All analyses will be performed in SAS v9.4 (SAS Institute, Cary, NC). [name] will perform analyses under the direct supervision of [name] and Drs. [name] and [name].

Aim 1. Evaluate the fidelity and efficacy of the TEAM intervention to promote healthcare provider counseling, medication reconciliation, and safe regimen use among adults taking complex Rx regimens.

Quantitative analyses will be performed using SAS v9.4 (SAS Institute, Cary, NC). To ensure adequate balance across treatment arms, baseline outcomes and potential confounders including socio-demographic characteristics, comorbidities, regimen complexity, health literacy

STU#: STU00209066

level will be compared using ANOVA models and χ^2 tests, as appropriate. Variables found to have significant differences ($p < .05$) across treatment groups will be entered as covariates in the generalized linear mixed models (GLMMs) used for formal analyses as described below. Treatment arm will serve as the primary independent variable. Analyses will be performed using PROC GLMMIX in SAS (v.9.4). A binary variable will be included in the model to denote the intervention group vs. usual care. As we will use stratified randomization by site, we will include in the GLMM an indicator variable for site and any potential confounding covariates noted in the descriptive studies. For outcomes assessed for each medication, 2-level GLMM will be used with medications nested in participants. Additionally, as there may be some effect of provider on adherence, we will explore the effect of any PCP by including provider as a random-effect. Using similar models as described above, we will assess the impact of TEAM on clinical markers (HbA1c, blood pressure, cholesterol) among patients with diabetes and hypertension.

Aim 2. Explore patient, healthcare provider (pharmacist, prescriber), community pharmacy and/or primary care practice barriers to implementation.

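### If listed drugs that the patient does not take are scored as incorrect, TEAM's edits to the EHR list can raise its correct-dosing rate with no change in patient behaviour

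*Combined protocol and SAP*

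**What the plan says.** - **Scored list (section 5.5, dosing errors).** The list is rebuilt every time the patient is interviewed: "RCs will review medications reported as taken by the patient and those listed in the EHR to create a final list of medications". The sentence goes on to describe these as the drugs prescribed to the patient, not the drugs taken. The patient then reports the last 24 hours drug by drug. "Data from this exercise will be used to assess correct dosing (yes/no) based upon the instructions for each medication". Where use differed from the prescription, the interviewer asks questions "to determine the reason for not taking the medication as prescribed (i.e. forgetfulness, ran out of medication".
- **TEAM's edits (sections 4.1 and 4.2).** Write access lets the TEAM pharmacist work on the list by "requesting the removal or discontinuation of prescribed drugs that patients report they are no longer taking" and by "adding medications omitted from the ACCESS primary care provider's list". Proposed changes carry a note, "requiring the prescriber to acknowledge the note and update the list". The pharmacist may instead "mark in the medication list if the patient reports not taking it at this time even though it is prescribed". The review should ideally be done one month after baseline and before the 2-month interview.
- **Usual care (section 5.3).** Pharmacists keep read-only access and unchanged workflows. Proactive review is allowed but described as rare.
- **Model (section 17.1).** For outcomes measured on each drug, "2-level GLMM will be used with medications nested in participants". The model has terms for arm, site and imbalanced baseline variables, with provider explored as a random effect. No term or rule concerns how the drug list was formed.
- **Related text (section 5.5).** Coordinators identify drugs no longer taken, and listed but untaken drugs are counted as commissions under Medication Reconciliation. Neither statement says whether those drugs stay in the dosing denominator.

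**The concern.** The drugs that enter the dosing model are those on a list made after randomisation, and the intervention can shorten that list in one arm. A drug that a usual-care patient has stopped but that remains in the EHR could count as a dosing error. The same drug, in a TEAM patient whose prescriber has acted on the pharmacist's request, would not be there to be scored. TEAM's additions do not offset this, because drugs reported by the patient are on the interview list anyway.

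Safe regimen use is part of the Aim 1 efficacy claim. A cleaner list is a genuine TEAM benefit, but the commissions outcome already captures it. If it also moves the dosing outcome, a change in record-keeping could be read as a change in how patients take their drugs.

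**Working it through.** The plan gives no figure to reproduce here. It states 120 patients, 60 per arm (2 × 60 = 120), with no effect size, dosing rate or drug count behind that number. The check therefore asks what the scoring would do if patients behaved identically in both arms.

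**Inputs**
- From the plan: 60 per arm, at least 5 prescribed drugs per patient (section 9.1), and the list edited in TEAM before follow-up.
- Assumed: *m* listed drugs in usual care, *u* of them untaken, *c* = share correctly dosed among drugs taken, *f* = share of untaken drugs removed in TEAM.
- Section 2.3 says 3 of 4 ambulatory patients may have inaccurate lists. That makes *u* > 0 plausible but does not give its value.

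**If untaken listed drugs are scored as incorrect**
- Usual care: c(m − u)/m
- TEAM: c(m − u)/(m − f·u)

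With m = 8 and c = 0.80:

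| u | Usual care | TEAM, f = 0.5 | TEAM, f = 1 |
|---|---|---|---|
| 1 | 5.6/8 = 70.0% | 5.6/7.5 = 74.7% | 5.6/7 = 80.0% |
| 2 | 4.8/8 = 60.0% | 4.8/7 = 68.6% | 4.8/6 = 80.0% |

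The spurious difference is +4.7 to +10.0 points with one untaken drug and +8.6 to +20.0 with two. Over m = 5 to 10, u = 0.5 to 2 and f = 0.25 to 1, with c = 0.80, it runs from +1.0 point (m = 10, u = 0.5, f = 0.25: 7.6/10 = 76.0% against 7.6/9.875 = 77.0%) to +32 points (m = 5, u = 2, f = 1: 2.4/5 = 48.0% against 2.4/3 = 80.0%).

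**If untaken drugs are dropped in both arms**

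Both arms score c(m − u)/(m − u) = c, so the difference is 0.

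**Simulation with no behavioural effect**

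Settings were 60 per arm, 3,000 runs per setting, about 7 taken drugs per patient, about 80% correct, and a patient random effect with SD 1 on the logit scale. The test was a cluster-robust comparison of proportions at two-sided 0.05. It stands in for the planned GLMM, and the 0.05 level is assumed because section 17.1 states none for outcomes.

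| Scoring | Rejection rate |
|---|---|
| Follow-up list, untaken scored incorrect, mean 1 untaken, half removed | 24.6% |
| Same scoring, over mean 0.5 to 2 untaken and 25% to 100% removed | 6.6% to 99.4% |
| Full baseline list in both arms | 4.6% to 5.9% |
| Only drugs taken, both arms | 4.5% to 5.2% |

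**The case against.** The strongest reply is that the inflation rests on a scoring rule that the plan does not contain. Section 5.5 has coordinators identify drugs no longer taken, refers to a final set of medications, and counts listed but untaken drugs separately as commissions. One fair reading is that such drugs are dropped before dosing is scored, in both arms, and then nothing is left to correct. Removal is also only a request that needs prescriber action, some untaken drugs are marked rather than removed, and the one-month timing is an aim. The drug counts and rates above are assumptions.

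All of that stands, and it makes the point conditional. It does not dispose of it. The dosing paragraph defines the list by what is prescribed and asks why a drug was not taken as prescribed, so untaken drugs can be on the recall list. Coordinators have access to arm assignment (section 5.4), which is a poor setting for an unwritten rule. Partial removal is covered by f below 1.

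Dropping untaken drugs at follow-up also leaves some selection after randomisation. TEAM offers help when patients report missed doses or early discontinuation (section 4.2). A drug resumed for that reason would enter TEAM's denominator while its usual-care counterpart stayed out, and the bias could then run the other way.

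A reader might also infer that all medication outcomes are affected. The documents do not support that. Ask-12 is a survey, and PDC is computed from pharmacy records within drug class, so neither uses the interview list. Knowledge is asked about each of the patient's drugs, so its denominator may shift. But not taking a drug does not make an answer about its purpose or risks wrong, and no knowledge effect was calculated.

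**Conclusion.** The point holds in conditional form and for correct dosing. The scored list is formed after randomisation, TEAM can edit it in one arm before follow-up, and nothing in the plan prevents the denominator from differing by arm. If untaken listed drugs score as incorrect, identical behaviour gives 70.0% in usual care against 74.7% to 80.0% in TEAM, assuming 8 listed drugs, 1 untaken, 80% correct among those taken, and half to all of the untaken drugs removed. If they are dropped in both arms, the effect is zero.

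It would be tempting to conclude that TEAM's dosing result will be inflated, or that a false-positive rate near 25% should be expected. The documents support neither. They leave the scoring open and give no count of untaken drugs, and the simulated rates come from a stand-in test under assumed inputs. What they do support is that, as written, a dosing difference could not be attributed to patient behaviour with confidence. This should be fixed before analysis.

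**What to change.** Keep the planned two-level GLMM and make these additions.

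1. State one rule for scoring a listed drug that the patient does not take, and apply it in both arms.
2. Pre-specify a sensitivity analysis of correct dosing over a list fixed at baseline in both arms: the chronic drugs on the baseline final list that the patient reported taking at baseline. Drugs untaken at baseline count only as commissions.
3. Have the 2-month interviewer ask about every drug on that fixed list, including any no longer in the EHR.
4. Keep drugs stopped by a prescriber in the fixed denominator. Report the results with these drugs counted both ways (as correct and as incorrect), and give their number by arm.
5. Interpret a dosing benefit as a change in patient behaviour in the light of this analysis. It need not be a formal condition for the claim in a 120-patient pilot.

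Item 4 matters because TEAM's removals are completed by the prescriber. If prescriber-stopped drugs left the denominator, the bias could return: with 8 listed drugs, 1 untaken and all such drugs removed, the comparison is again 5.6/8 = 70.0% against 5.6/7 = 80.0%. Restricting the list to drugs taken at baseline keeps already-stopped drugs out of both arms from the start. With unchanged behaviour both arms then score the same.

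The cost is a few more recall questions at 2 months and one further model run. The limitation is that drugs started or resumed after baseline fall outside this analysis; the planned analysis still covers them.

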4.2 Medication Review by Telephone

The Walgreens Research Analytics Team will be notified of all patients randomized to the TEAM intervention on a weekly basis. They will then generate an Adherence Report for all medications in the predetermined six therapeutic medication classes, which will include rolling 12 month PDC per medication. This Adherence Report will be sent directly to the Walgreens pharmacist prior to initiating the CMR by phone. S/he will retrieve contact information for the patient via the EHR and attempt to initiate an introduction via telephone, wherein the pharmacist will explain his/her role, and establish a time (on the introductory call or scheduled for a later date) to perform a medication review. This is estimated to take between 10-45 minutes, depending on the size and complexity of the patient's regimen. The pharmacist will begin by reconciling the Epic EHR medication list with the patient, matching up what the patient is currently taking, what has been discontinued by a prescriber, what is still prescribed but the patient is not taking (and why), and identifying any omissions. Each medication will be reviewed, either in the list or identified by the patient, including a brief review of how patients take the medicine to ensure safe use. Patients will also be probed on whether they are experiencing any symptoms that could be signs of an adverse drug event (ADE). Pharmacists will address any questions or concerns patients may have about their medicine (e.g. side effects, treatment alternatives, dietary restrictions, cost, 90 vs. 30 day scripts), and assess patients' adherence. If missed doses or premature discontinuation is reported, problems (e.g. cost, forgetfulness) will be discussed and assistance offered (e.g. synchronization requests, pill box, reminders).

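### The outcome named proportion of days covered is defined as a summed supply ratio with no stated window, yet is cut at a threshold meant for PDC; the definition in section 5.5 needs replacing

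*Combined protocol and SAP*

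**What the plan says.** Section 5.5 (Measurement, Medication adherence) plans two adherence measures, the Ask-12 survey and PDC from pharmacy records. For the second, "PDC will be calculated by summing the number of days' supply obtained by a patient during a given time period" and then "dividing by the number of days for which the medication was prescribed". Adherence is assessed within drug class, and after a switch within a class "all prescriptions will be summed in the numerator". The result is analysed as a continuous variable and as yes/no, the latter as "PDC at disease-specific threshold based on Pharmacy Quality Alliance (PQA) standards". No numeric threshold is given.

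On the source, the same paragraph says that "PDC data will be automatically obtained from Walgreens as part of the TEAM study". It does not say how Walgreens computes the figure, or whether Walgreens or the study team does the calculation.

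The only PDC period stated anywhere is in section 4.2: "rolling 12 month PDC per medication". That figure belongs to the Adherence Report sent to the TEAM pharmacist before the medication review. A further report follows later: "At 6 months, the Walgreens Research Analytics Team will send an additional Adherence Report for patients in the TEAM intervention". Neither is called the outcome, and both concern TEAM patients only. The Analysis Plan (17.1) adds no rule for PDC.

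**The concern.** A proportion of days covered counts each day once and cannot exceed 1. A sum of days' supply does neither. The plan gives no cap, no overlap rule other than summing, no truncation at the end of the window, no rule for supply on hand at the start, and no window. The trial has time points at 2, 6 and 12 months (sections 5.2 and 8.0), and none is tied to PDC.

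At stake is the yes/no outcome most directly. A patient with long uncovered gaps can be called adherent. Depending on where the window starts, a well-covered patient can be called non-adherent. The value also depends on a window that has yet to be chosen.

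**Working it through.** The documents give no PDC value, effect size or numeric threshold, so there is no plan figure to reproduce. The check applies two rules to the same fill histories.

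**Rules**
- Section 5.5 ratio = sum of days' supply of all fills dated inside the window / days prescribed.
- Days covered = distinct days in the window with any drug of the class on hand / days in the window.

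**Assumptions.** The drug is prescribed throughout the window, so the two denominators are equal. The cut is 0.80. The documents do not give the PQA figure; section 2.1 mentions 80% of prescribed doses, but only as background. The windows of 60, 180 and 365 days are approximations to the trial's 2-, 6- and 12-month points.

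**1. A patient with every day covered (true value 1.00)**

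| Fills, all on time | 60 days | 180 days | 365 days |
|---|---|---|---|
| 30-day | 60/60 = 1.00 | 180/180 = 1.00 | 13 × 30/365 = 1.07 |
| 90-day | 90/60 = 1.50 | 180/180 = 1.00 | 5 × 90/365 = 1.23 |

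The ratio exceeds 1 and changes with the window, although behaviour is identical.

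**2. Supply running past the window.** 90-day fills on days 0, 130, 250 and 355, over 365 days.
- Ratio: 4 × 90/365 = 360/365 = 0.99.
- Covered: 90 + 90 + 90 + 10 = 280; 280/365 = 0.77.

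**3. Within-class switch.** A 90-day supply on day 0, a switch on day 20 to 90 days of another drug in the class, then nothing, over 180 days.
- Ratio: (90 + 90)/180 = 1.00.
- Covered: days 0 to 109, so 110/180 = 0.61.

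**4. Supply on hand at a calendar start.** 90-day fills on days -10, 100, 205 and 310, over 365 days.
- Ratio: only three fills fall inside the window, so 270/365 = 0.74.
- Covered: 80 + 90 + 90 + 55 = 315; 315/365 = 0.86.

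**5. A history where the rules agree.** Ten on-time 30-day fills from day 0: both give 300/365 = 0.82.

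Cases 2 to 4 change class at 0.80. Case 2 does so for any cut above 0.767 up to 0.986, case 3 above 0.611 up to 1.00, and case 4 above 0.740 up to 0.863. All three therefore change class for any cut above 0.767 up to 0.863.

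**Direction.** If the window opens at a fill and nothing is left over from before, every covered day comes from supply counted in the numerator. The ratio then cannot fall below days covered, and the error is upward only. Case 4 needs a window that opens at some other point.

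**How often? Illustration only.** I simulated one drug with exponential refill gaps over 365 days at the 0.80 cut. At 75% mean coverage the two rules disagreed on who is adherent as follows:

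| Window start | 30-day fills | 90-day fills |
|---|---|---|
| Calendar date | about 17% | about 27% |
| At a fill | about 30% | about 17% |

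With a calendar start, disagreement on 30-day fills was 1.3% at 60% coverage and 0.2% at 90%. On 90-day fills it was 7% at 60% and 41% at 85%. Each figure is one scenario. Coverage, refill length, window start and cut all drive the answer, and the documents fix none of them.

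**The case against.** The strongest reply is that Walgreens supplies the PDC. If its feed is already computed day by day, the analysed variable may be a true PDC and only the prose is wrong. That stands as a limit: misclassification is conditional on the section 5.5 formula being applied. It does not clear the text, because no algorithm is stated and a day-level feed would contradict the formula printed beside it.

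Second, section 5.5 says these measures have been used in the team's published studies, and it cites PQA standards. Working rules may exist there. But the PQA reference is attached to the threshold, prior use supplies no window for this trial, and the instruction to sum all prescriptions after a switch is explicit.

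Third, the continuous version may suffer less. In the calendar-start simulation the mean is 0.750 under either rule. This stands for that window only. When the window opens at a fill, the simulated means at 75% coverage are about 0.79 against 0.76 on 30-day fills and 0.89 against 0.79 on 90-day fills.

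A reader might also infer that the formula favours TEAM, because TEAM calls may cover "side effects, treatment alternatives, dietary restrictions, cost, 90 vs. 30 day scripts" and refill synchronization, while pharmacy routines for controls stay as they are (section 5.3). The route is plausible, but no section says how many patients would change refill length or when. Neither the size nor the direction of a difference between arms can be established.

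**Conclusion.** The definition is wrong as written. A summed supply ratio carries the name of a proportion of days covered and is cut at a threshold for that proportion, with no outcome window stated. This rests on the text of section 5.5 and on exact arithmetic. Individual errors can be large: 0.99 against 0.77, 1.00 against 0.61, and 0.74 against 0.86 with a calendar start. Reclassification in these examples rests on the assumed 0.80 cut, though any cut above 0.767 up to 0.863 gives the same result in all three.

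The documents do not support three further steps: that the analysed data will certainly be misclassified, that a particular share of patients is affected, or that the comparison between arms is biased.

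The scope is one of two adherence measures in a 120-patient pilot. Section 3.0 names no clinical primary outcome. This should be fixed before analysis; it does not undermine the trial as a whole.

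**What to change.** In section 5.5, replace the formula with: distinct calendar days with any drug of the class on hand, divided by the days in one stated post-randomisation window. The 12 months to the final EHR pull in section 8.0 is one candidate. Compute it from Walgreens fill-level records with the same code in both arms, and state:

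- early refills of the same drug are carried forward;
- overlap after a within-class switch is counted once;
- supply past the end of the window is dropped;
- how supply on hand at the start is counted;
- the value is capped at 100%;
- the numeric threshold used for each class;
- this variable, and not the pharmacist's Adherence Report, is the outcome.

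A cap alone is not enough: it would leave cases 2 to 4 misclassified.

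The cost is a paragraph of text and some programming. Sections 5.2 (Evaluation Phase) and 5.6 already plan to use pharmacy records and Walgreens fill data, though a fill-level extract for both arms must be confirmed. One limit remains: the yes/no version still varies with refill length. In a simulation at 75% mean coverage with a calendar start, 22% of patients on 30-day fills and 35% on 90-day fills reached 0.80 by days covered.
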